7.3.7. GP IIb/IIIa inhibitors

GP IIb/IIIa inhibitors are strongly discouraged in subjects adequately pre-loaded with an ADP antagonist (clopidogrel, prasugrel, or ticagrelor), especially if bivalirudin is used. GP IIb/IIIa inhibitors may be used, however, in subjects with large amounts of thrombus, or for thrombotic or ischemic complications arising during the procedure (provisional or bail-out use) – e.g. for refractory thrombus or no reflow resistant to repeat balloon dilatation and intracoronary use of nitroprusside or calcium channel blockers in the absence of a mechanical complication. Provisional GP IIb/IIIa inhibitors may not be used for "soft" indications such as lesion haziness or a small dissection as their use in these situations will increase bleeding complications, without clear benefit.

7.4. **Procedure – CABG**

The treatment for subjects randomized to CABG is as follows:

7.4.1 Optimal CABG Requirements

• *Conduct of Surgery.* Coronary artery bypass grafting may be performed with or without the assistance of cardiopulmonary bypass, depending on the expertise of the center. Robotic surgery techniques may not be used.

On-pump, surgical revascularization may be performed with an arrested heart or beating

heart strategy. Cannulation for cardiopulmonary bypass should be ascending aortic for arterial return, unless there is ascending aortic atherosclerosis or dilatation (\geq 4 cm in diameter), and right atrial for venous drainage. In cases of aortic atherosclerosis or dilatation, an alternate arterial cannulation strategy must be performed (see below). Cardiopulmonary bypass blood flow should be maintained at least at 2.0 liters/m²/minute. Systemic arterial blood pressure should be increased in the elderly and in those with cerebrovascular disease to ensure adequate cerebral blood flow. During cardiopulmonary bypass the subject's temperature may be cooled or allowed to drift down as determined by local practice. Use of a single cross-clamp technique for subjects undergoing CABG on CPB is strongly recommended and multiple applications of an aortic clamp is strongly discouraged. When weaning from cardiopulmonary bypass it is recommended that the subject be normothermic.

Sites will be advised to follow their own insulin protocols for glucose level management intra-and postoperatively if these are consistent with the STS practice guidelines. If no guidelines exist, then sites will be advised to follow an insulin protocol similar to the one included in Appendix I.

In off-pump and on-pump beating heart surgery, coronary stabilization devices must be used. Coronary artery exposure and cardiac manipulation may be performed with apical suction positioners and/or pericardial sutures. Intravascular shunts may be used to prevent ischemia and allow for hemostasis during performance of the distal anastomoses. Proximal vessel loops may be used to obtain hemostasis during construction of the distal anastomoses or placement of intravascular shunts. Distal vessel loops are to be avoided whenever possible. The use of a humidified blower during the performance of the distal anastomoses to improve visibility is highly recommended. Every effort should be made to keep the subjects normothermic during off-pump revascularization.

After completion of proximal and distal anastomoses, graft patency assessment is strongly recommended with either transit time Doppler flow measurements or with intra-operative angiography with immunofluorescence or standard radiographic angiography. If a bypass graft is determined to be functioning poorly, the graft should be evaluated and revised.

- *Aortic Assessment.* It is strongly recommended that intra-operative assessment of the ascending aorta by transesophageal echocardiography and/or epi-aortic echocardiography be performed. Aortic assessment should be performed prior to manipulation, cannulation, or clamping of the ascending aorta. If ascending aortic atherosclerosis or dilatation is identified, a surgical strategy must be used that does not manipulate, cannulate, or clamp the atherosclerotic or dilated aorta. For on-pump revascularization a strongly recommended option is alternate site arterial cannulation (axillary or femoral artery) with no ascending clamping, and for off-pump revascularization a strategy with a no-touch aortic technique should be used as a last resort for subjects with ascending aortic atherosclerosis. Locally approved proximal aortic connectors and facilitators (that do not involve aortic clamping) may be used to perform proximal anastomoses.
- *Cardioplegia for On-Pump, Arrested Heart Surgery.* Intermittent, cold blood cardioplegia is the preferred myocardial protection strategy for on-pump, arrested heart surgery. However, intermittent cold crystalloid cardioplegia or continuous warm blood cardioplegia is allowed if local standard of care. Cold blood cardioplegia should be administered initially at 10 to 15

cc/kg to arrest and protect the heart, and then re-administered every 20 to 30 minutes at a minimum of 5 cc/kg. Delivery of cardioplegia should be initially antegrade to arrest the heart in the absence of important aortic insufficiency. If important aortic insufficiency is present and antegrade delivery of cardioplegia is not feasible, cardioplegia should be administered retrograde to arrest the heart and additional right ventricular protection methods should be performed, such as ice slush to the surface of the right ventricle and cardioplegia administered via the completed bypass graft to the right coronary artery system. During the remainder of the cross-clamp period, cardioplegia may be administered antegrade, retrograde via a coronary sinus catheter, and/or via completed saphenous vein grafts. If available, a nutrient rich hot shot given prior to removing the aortic cross-clamp is highly recommended.

• Conduit Selection. Arterial grafts are the preferred conduits for coronary revascularization. It is strongly recommended for all subjects to have the left internal thoracic artery used to graft the left anterior descending coronary artery system. In most cases this may be the left internal thoracic artery. In subjects less than seventy years of age, additional arterial grafts are highly recommended. The right internal thoracic artery is the preferred second arterial graft, and should be used to graft the next most important and stenotic coronary artery system. It may be used as an in-situ graft or free graft. Other arterial grafts that may be used in this study include the radial, in-situ gastroepiploic, and free inferior epigastric arteries. When using the radial artery as a bypass graft, it should be preferentially used to revascularize a left coronary artery system branch with severe (>70%) stenosis. The in-situ gastroepiploic artery may be used to graft severely stenotic (preferentially occluded) branches of the right coronary artery or posterior descending of a left dominant system. The inferior epigastric artery is best used as a "Y" or "T" graft.

Saphenous vein grafts may be used for coronary revascularization in the study. Since internal thoracic artery grafting of the left anterior descending is standard of care for surgical revascularization, saphenous veins may be used to bypass the left anterior descending only when the left internal thoracic is an inadequate conduit.

Although arterial grafts are the preferred conduit, each center should use a conduit revascularization strategy that they are experienced and comfortable performing. When selecting conduits, the effects of native coronary competitive blood flow must be considered.

Details of non-use of arterial grafts and non-use of internal mammary artery grafts including the reasons for such non- use will be recorded in the EXCEL trial eCRF.

• Intraoperative Transesophageal Echocardiography Assessment. It is highly recommended that intraoperative transesophageal echocardiography be performed prior to cannulation to assess left ventricular function, cardiac valves, and ascending aorta. For subjects with intraoperatively identified important valve dysfunction or aortic aneurysmal disease, the surgeon may repair or replace the valve or aorta as deemed necessary. Intraoperatively, after coronary revascularization is complete, it is strongly recommended that transesophageal echocardiography be used to assess for new ventricular wall abnormalities. If new ventricular wall abnormalities are identified, then the bypass graft supplying that myocardial area should be evaluated and revised if necessary.

7.5. Completeness of Revascularization

All ischemic myocardial areas, such as those subtended by coronary arteries with visually assessed \geq 50% diameter stenosis, should be revascularized.

For subjects randomized to PCI: In prior PCI vs. CABG trials, the determination of and execution of "completeness of revascularization" strategy has been an important consideration. In this trial, the philosophical approach is to perform PCI of all significant ischemia-producing lesions as opposed to all lesions which appear to be significant by angiographic visual assessment, especially if the angiographic lesions are 40-70% diameter stenosis. Moreover, it is strongly recommended that PCI is performed only in ischemia-producing lesions, in most cases not treating non ischemia-producing lesions. Ischemia-producing lesions are defined as those which (1) are \geq 70% angiographic diameter stenosis (visually assessed), or if <70% diameter stenosis, are either (2a) associated with noninvasive functional evidence of ischemia in the territory of the lesion (not explained by another coronary stenosis), and/or (2b) intra-procedure FFR \leq 0.80 (note FFR procedure guidelines), and/or (2c) IVUS minimal luminal area \leq 4.0 mm² (for non left main lesions) with plaque burden >60% (note IVUS procedure guidelines).

For subjects randomized to CABG: Since all subjects in this study have important ULMCA stenosis, according to contemporary surgical standards, all subjects should have at least one bypass graft to the left anterior descending coronary artery system and a second graft to circumflex coronary artery system. All coronary arteries with \geq 50% stenosis and \geq 1.5 mm in diameter should be revascularized.

7.6. Post-Procedure Assessments and Medications

Following the procedure, mandated medication is specified below; beyond that, the subject will be treated in accordance with hospital standard of care.

7.6.1. Laboratory Assessments

The laboratory assessments need to be obtained according to the Schedule of Events included in Section 7.1.

7.6.2. Post-PCI Medications

Aspirin. Mandatory dosing with aspirin will be \geq 75 mg post-PCI per day in the hospital, and then aspirin \geq 75 mg per day indefinitely. Daily aspirin must be given for the duration of the trial. Aspirin must not be discontinued for CABG or other reasons unless absolutely necessary.

ADP antagonists. Chronic daily ADP antagonist therapy is mandated for at least one year after PCI in subjects who received a ULMCA DES, with the choice of agent left to the discretion of the investigator, either:

• clopidogrel 75 mg per day, or 150 mg per day for 7-30 days then reduced to 75 mg per day, unless clopidogrel hyporesponsive;

• prasugrel 10 mg per day (5 mg per day may be used in patients <60 kg in body weight or in other circumstances, but in general the 5 mg per day prasugrel dose is discouraged given

minimal clinical experience with this prescribed amount);

• ticagrelor per labeling and recommended guidelines if approved by the local regulatory authorities during the treatment period of this protocol.

"Hypo-responders" to anti-platelet therapy based on point of care testing are managed according to local standard of care. A daily ADP antagonist must be given for at least one year in the absence of major complications, and is recommended for the duration of the trial in the absence of major bleeding or other complications.

ADP antagonists must not be discontinued within the first year after DES implantation unless absolutely necessary for major bleeding, major trauma, or major surgery necessitating discontinuation of antiplatelet therapy (e.g. intracranial surgery). Many surgeries can safely be performed while the subject is on dual antiplatelet therapy. If a subject on dual antiplatelet therapy requires surgery, strong consideration should be given to performing the surgery without antiplatelet agent discontinuation. If a particular dual antiplatelet therapy must be discontinued, a GP IIb/IIIa bridging strategy up until the time of surgery may be considered, followed by reloading of the ADP antagonist as soon as possible post surgery.

Statin therapy. See Section 22.2 for recommendations for statin use after PCI.

Other medications. For medication use post PCI, see Section 22.2.

7.6.3. Post-CABG Medications

Aspirin (\geq 75 mg) must be given within six hours after surgery intravenously, orally, rectally, or via a nasogastric tube if there is no important bleeding (\leq 50 cc/hr), and daily for the duration of the trial. All subjects should be treated postoperatively with daily statins and beta-blockers, unless contraindicated, see Section 22.2.

Beta-blockers are recommended for prophylaxis of post-operative atrial fibrillation. Amiodarone may be considered for subjects in whom beta-blockers are contraindicated and as therapy for postoperative sinus rhythm control. For subjects receiving amiodarone prophylaxis for atrial fibrillation, amiodarone should be continued for five days postoperatively.

It is recommended that ACE inhibitors be given in subjects with depressed left ventricular function.

Clopidogrel is not required but may be administered as per local standard of care in subjects with saphenous vein grafts or in those who underwent off-pump surgery.

7.6.4. Post-Operative Atrial Fibrillation – CABG

Post-operative atrial fibrillation should be treated with either rate control and anticoagulation, or chemical or electrical cardioversion. Subjects being treated with rate control and anticoagulation should be treated with warfarin and may be bridged with heparin as per local protocol. Subjects undergoing cardioversion may undergo cardioversion without anticoagulation if the duration of atrial fibrillation is less than 36 hours. Subjects undergoing cardioversion where the duration of atrial fibrillation is greater than 36 hours should be adequately anticoagulated with either heparin or warfarin as per local practice. If atrial fibrillation recurs or is resistant to cardioversion,

anticoagulation with warfarin with or without heparin bridging is strongly recommended. Warfarin anticoagulation should be continued as per local practice, but at a minimum until atrial fibrillation has resolved. Subjects on warfarin anticoagulation for atrial fibrillation should be maintained with an INR of 2.0 to 2.5.

8. EVALUATION OF SAFETY AND EFFECTIVENESS

Safety and efficacy will be evaluated at several timepoints throughout the trial as described in the Schedule of Events.

8.1. Laboratory Tests, ECGs, and Other Measures

Tests will be performed periodically on all subjects as follows (Section 7.1, Schedule of Events):

8.2. Clinical Follow-up

Subjects will have clinical follow-up as a telephone contact or office visit, at the time points listed below. Day 0 is the date of the randomization assignment which can be on the same date or earlier than the date of the randomized procedure. All adverse events (AE) will be recorded from Day 0. Patient follow-up will occur from the day of randomized procedure as shown below. Office visits are strongly recommended for the annual clinical follow-up. If that is not possible, phone contact with subject or subject's local physician is acceptable. As a last resort, notification of death by civil registry will be accepted.

- 30 ± 7 days (office visit preferred)
- 6 months \pm 14 days (telephone contact or office visit)
- Visits at 1, 2, 3, 4, and 5 years with windows of -30 days, +60 days (office visit preferred)
- Potential visits:
 - Yearly visits at 6, 7, 8, 9, and 10 years with window of-30 days, +60 days (office visit preferred)

All efforts must be made to obtain follow-up information on subjects who have visited a clinic or hospital, underwent procedures or have been treated for adverse events in a non-study-related hospital(s). Non study hospital related material will be collected and reviewed at the study coordinating centers. All follow-up angiograms must be collected (whether at the study hospital or an outside hospital) and sent to the angiographic core laboratory for independent analysis.

The following data will be collected at 30 days, 6 mo, 1 year, 2 years, 3 years, 4 years and 5 years follow-up time points (and potential 6-10 year visits).

• Data regarding adverse events (with related laboratory tests results), including but not limited to death, MI, stroke, TIA, bleeding, renal insufficiency, repeat revascularization procedures, repeat hospitalization for any reason, ECGs, details of any subsequent repeat coronary angiography and results of such, if applicable.

- Details of any subsequent coronary interventions (for example, repeat PCI or CABG). The physician must record in the source documents whether a revascularization was carried out during the period between the index procedure and the follow-up visit. The physician must then document whether the revascularization was based on clinical signs and symptoms and available ancillary data and whether the procedure was ischemia driven according to the definition specified in this protocol (Refer to Section 16, Appendix A).
- Compliance to protocol-required medications
- Use and changes in chronic concomitant medications (Refer to Section 16, Appendix A).

Additional Follow-up Visits

Additional subject visits may occur as clinically warranted. The same information as specified in Section 8.2, Clinical Follow-up, will be collected.

To support the 3 year endpoint analysis, clinical sites will be asked to obtain the 3 year adverse event status on all subjects. Therefore, an adverse event (AE) check should be performed in order for data up to 3 years (365 days*3=1095 days) from date of randomization to be established equally in both arms. The AE check will commence the day after the 2 year follow-up of the last subject enrolled. At this time, all clinical sites must contact subjects to collect AE information if one of the following has occurred:

• Subject had a 3 year visit >28 days prior to 1095 days; or

• Subject has completed their 2 year visit but has not yet completed the 3-year visit, and followup is beyond 730+28 days.

For subjects who have completed visits at \geq (1095 – 28= 1067) days, no further contact is needed concerning the AE check.

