6.7. Subject Discontinuation

Every subject should remain in the trial until completion of the required follow-up period. However, a subject's participation in any clinical trial is voluntary and the subject has the right to withdraw at any time without penalty or loss of benefit. Should this occur, the reason for withdrawal must be recorded in the source documentation. Conceivable reasons for discontinuation may include, but not be limited to, the following:

• **Subject Withdrawal:** Subject participation in a clinical trial is voluntary and the subject may discontinue participation (refuse all subsequent testing/follow-up) at any time without loss of benefits or penalty.

• **Lost-to-Follow-up:** Subject does not complete the scheduled follow-up visits but has not officially withdrawn from the trial (does not apply to missed visits). Site personnel should make all reasonable efforts to locate and communicate with the subject, including the following, at each contact time point:

- A minimum of two telephone calls to contact the subject should be recorded in the source documentation, including date, time, and initials of site personnel trying to make contact.
- If these attempts are unsuccessful, a letter should be sent to the subject.
- If the subject misses two consecutive scheduled contact time points and the above mentioned attempts at communicating with the subject are unsuccessful, the subject will be considered lost-to-follow-up.

Note: If a subject misses one or more of the follow-up contact time points this will be considered a missed visit. Subject may then return for subsequent visits.

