2.3 DESIGN OF THE STUDY

The randomized control portion of this study (that will be referred to as RCT) is a prospective, unblinded, randomized multicenter trial of approximately 1,900 subjects enrolled at approximately 165 US and OUS centers. Following diagnostic angiography demonstrating significant ULMCA disease and consensus of the local Heart Team (qualified participating interventional cardiologist and cardiac surgeon) that the subject meets the study entry criteria, subjects will be consented and randomized 1:1 to: a) PCI using XIENCE (N=950), or b) CABG (N=950). Follow-up for all randomized subjects will continue for five years with a potential for additional follow-up to 10 years. The primary endpoint will be assessed at least 2-years after the last subject is randomized, with a median follow-up duration in all subjects of at least 3 years.

All randomized subjects will have a follow-up telephone contact or office visit at 30 days, 180 days, and 1, 2, 3, 4 and 5 years following the index procedure. In addition, to minimize bias in the assessment of the primary endpoint, at the time the last randomized subject reaches the 2-year follow-up duration (730 + 28 = 758 days), an additional adverse event (AE) check will be performed in order for data up to 3 years (365 days*3=1095 days) from the date of randomization to be collected equally in both arms.

The AE check will commence the day after the 2-year follow-up duration of the last subject enrolled (i.e. 758 days), and will be completed prior to the database snapshot. At this time,

subjects with either of the following conditions should be contacted by each clinical site by phone or office visit to collect AE information:

- Subjects who have not yet completed the 3-year visit, unless the most recent follow-up was completed within 28 days of the AE check initiation; or
- Subjects who have completed a 3-year visit before day 1067 after randomization (i.e. >28 days prior to exactly 3 years [1095 days]).

For subjects who have completed any follow-up visit at \geq (1095 – 28= 1067) days, the AE check is not required.

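### The contact list for the 3-year adverse event check in Protocol 8.2 omits subjects with neither a 2-year nor a 3-year visit, contrary to the protocol's own aim and to the SAP

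*Protocol*

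**What the plan says.** Protocol 8.2 (Additional Follow-up Visits) opens with a broad aim: "clinical sites will be asked to obtain the 3 year adverse event status on all subjects". Protocol 4.2 repeats it. Section 8.2 then says that the check starts the day after the last subject's 2-year follow-up, and that sites have to contact a subject who meets one of two conditions. The first is an early 3-year visit, held before day 1067. The second, which is the one at issue, reads "Subject has completed their 2 year visit but has not yet completed the 3-year visit"; this condition applies only once day 758 has passed.

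For a subject with a visit at day 1067 or later, "no further contact is needed concerning the AE check".

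SAP 2.3 has two triggers as well. The early-visit trigger is the same in substance: "Subjects who have completed a 3-year visit before day 1067 after randomization". The other is wider: "Subjects who have not yet completed the 3-year visit, unless the most recent follow-up was completed within 28 days of the AE check initiation". SAP 3.7 repeats this wider rule. Neither SAP section mentions the 2-year visit as a condition. SAP section 5, which records changes from the protocol, does not list the difference.

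On the status of an absent subject, Protocol 6.7 says: "If a subject misses one or more of the follow-up contact time points this will be considered a missed visit". The subject may return for later visits. Loss to follow-up requires two consecutive missed contacts and failed tracing.

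**The concern.** A site coordinator carrying out the check will work from the list, because that is where the obligation is stated. A subject who missed the 2-year visit and has not yet had a 3-year visit is still in the trial under Protocol 6.7. That subject is not exempt under the day-1067 rule, yet is not on the list. Among subjects still in follow-up at that point, this is a group with a long unobserved interval.

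If no contact is made, the subject is censored at the last known contact (Protocol 9.1.8; SAP 3.4.3 and 3.8). Kaplan-Meier estimation then assumes that subjects who skip visits have the same later risk as those who attend. SAP 3.8 relies on this censoring and plans no analysis that tests the assumption. SAP 2.3 gives reducing bias in the primary endpoint as the purpose of the check, so the omission works against the reason for holding it.

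**Working it through.** **1. The plan's own figures.** The day counts hold: 365 × 3 = 1095, 1095 − 28 = 1067, 730 + 28 = 758. The sample size also reproduces. With 11% in each arm, a margin of 4.2%, one-sided alpha 0.025 and 80% power, n per arm = 2 × 0.11 × 0.89 × (1.960 + 0.842)² / 0.042² ≈ 872. Allowing for 8% loss, 872 / 0.92 ≈ 948, or 1896 in total against 1900 stated. The point disputes no design figure.

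**2. The two rules applied to each visit history.**

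| History at the check | Protocol 8.2 list | SAP 2.3 and 3.7 |
|---|---|---|
| 2-year done, 3-year not done, beyond day 758 | contact | contact, unless seen within 28 days |
| 2-year missed, 3-year not done | **not listed** | **contact, unless seen within 28 days** |
| 2-year missed, 3-year done before day 1067 | contact | contact |
| 2-year missed, visit at day 1067 or later | no contact needed | no contact needed |

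The rules part company on who must be reached in the second row only.

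**3. How many subjects.** The documents give no rate of missed 2-year visits, so I assume 2% to 5%. With uniform accrual over 29 months and the check starting when the last subject reaches 24 months, potential follow-up runs from 24 to 53 months. The share with 2 to 3 years is 12/29 = 41.4%, or 1900 × 12/29 ≈ 786 subjects. Subjects beyond 3 years have already had a 3-year visit due. If they attended, their status is known or the first trigger applies. If they could not be reached after two missed contacts, they count as lost, which the planned 8% already allows for. The gap is therefore 786 × 0.02 ≈ 16 to 786 × 0.05 ≈ 39 subjects over both arms.

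**4. Effect on the rate.** Further assumptions are constant hazard λ = −ln(0.89)/3 = 0.0388 per year, affected subjects last contacted at 1 year, and hazard multiplied by r = 2 or 3 after that.

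- The true 3-year risk for a subject who misses the visit is 1 − exp(−λ − 2rλ): 17.7% at r = 2 and 23.8% at r = 3, against 11%.
- The first-order understatement is 0.414 × (share missing) × (excess risk). At 2% and r = 2, this is 0.414 × 0.02 × 6.65 ≈ 0.055 points. At 5% and r = 3, it is 0.414 × 0.05 × 12.8 ≈ 0.26 points.
- The full Kaplan-Meier calculation includes the administrative censoring between years 2 and 3. It gives smaller values, because higher-risk subjects with 3 years of potential follow-up stay in the risk set while others leave it.

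| Missed 2-year visit | r = 1 | r = 2 | r = 3 |
|---|---|---|---|
| 2% | 0 | 0.04 | 0.08 |
| 5% | 0 | 0.11 | 0.21 |

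Entries are percentage points of understatement in one affected arm.

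**5. Effect on precision.** At the ordinary hazard (r = 1), the uncontacted subjects would cost about 0.8 events (2% missed) or 2.0 events (5% missed) of about 188, and about 0.2 or 0.4 points of power.

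**The case against.** The strongest reply is that the protocol already asks for these subjects to be followed. Sections 4.2 and 8.2 want 3-year status on everyone. Section 6.7 requires calls and then a letter at each contact point, and every attempt to follow all randomized subjects through five years. Section 11.5 has records reviewed for every subject in search of primary endpoint events. SAP 2.3.1 counts registry deaths for early drop-outs. The rule is also the same in both arms, so equal effects largely cancel in the difference.

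Much of this stands, and it rules out three stronger inferences a reader might draw:

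- **That only subjects with a completed 2-year visit are contacted.** The first trigger has no 2-year condition.
- **That subjects who missed the 2-year visit go untraced.** The provisions above say otherwise.
- **That all of them are censored at 1 year.** This would give about 0.13-0.26 points at 2% missed and 0.33-0.64 points at 5%. It is about three times too large, because it counts subjects who had already reached their 3-year visit.

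The reply does not close the gap. None of these provisions puts the omitted subject on the list for the check. Registry dates recover deaths but not infarction or stroke. Record review finds only what has reached the records, and a scheduled 3-year visit does not help if it falls after the snapshot.

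**Conclusion.** The point holds as an inconsistency. The Protocol 8.2 list does not deliver the section's own stated aim, and it is narrower than SAP 2.3 and 3.7 for subjects with neither a 2-year nor a 3-year visit. Those subjects may be censored at their last contact in the primary analysis.

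The likely size is small: about 16-39 subjects, and roughly 0.04-0.2 points of understatement in an affected arm, which is about 1-5% of the 4.2-point margin. This rests on uniform accrual, an assumed 2-5% missing the 2-year visit, last contact at 1 year, an assumed 2-3 times hazard afterwards, and no recovery of their events by any other route. With no excess hazard, the bias is zero.

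A reader might infer that the PCI-CABG comparison is biased. The documents do not support that. It would need missed visits, or their link to outcome, to differ by arm. An unblinded trial makes this possible, but nothing in the documents shows it.

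**What to change.** Replace the second condition in Protocol 8.2 with the SAP rule: contact every subject without a completed 3-year visit, expressly including those who missed the 2-year visit, unless the most recent follow-up fell within 28 days of the start of the check. Leave the first condition and the day-1067 exemption as they are. No sample size, margin or analysis changes.

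The cost is one amended bullet and, on the assumptions above, about 16-39 extra contacts. It has to be done before the database snapshot, because events missed at that point cannot be recovered for the primary analysis.
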